Administrative supplement: The administrative supplement presents minimal risks to participants. The DD process will not impact usual RWPA services (e.g., receipt of mental health services). Risks to participants include potential violation of confidentiality. However, the level of risk is not substantially increased by the conduct of the proposed study, relative to the risks of regular participation in RWPA services (which involves routine client-level data reporting to the DOHMH) or regular participation in the HIV Planning Council's Consumers Committee. The study team will not collect individual health-related data or personal identifiers, except for minimal contact details and the client's eSHARE ID, to be retained only as long as needed for the planning and confirmation of session attendance and release of participant incentives. Only first names or chosen nicknames will be used in follow-up communications, and only after participants have agreed to participate in the DD experiment. In addition, the strictest, state-of-the-art data security and privacy measures (already in place as part of routine program implementation and monitoring, routine conduct of NYC HIV surveillance, and interviewing procedures used in prior research by this study team) will be employed to ensure the confidentiality of all participant information shared and analyzed as part of this protocol. However, as with all studies involving individual-level data, there is always a slight risk of loss of privacy for study participants. Procedures put in place to maintain privacy and meticulously followed to minimize risk include: intensive training of study staff on participant confidentiality; maintenance of detailed field security protocols and standards of practice related to physical and electronic protections of participant data; and (in the case of individual surveys) the use of study identification numbers (rather than personal identifiers) on study documents and analytic datasets. In this study, only site-level or program-level data will be merged with evaluation surveys and qualitative data. Risks include the loss of privacy and/or confidentiality during data collection and analysis, and negative or uncomfortable feelings brought up during DD sessions or evaluation. We will mitigate these risks by hiring facilitators to lead small groups who are specifically trained in equity and cultural humility. Sessions will also be guided to home in on issues related to data privacy, data sharing, and client autonomy, rather than exploring clients' own service needs or personal health care or illness experiences.

P. Potential Benefits

This description should also be based on accrued data from related studies that have been completed. Anticipated benefits of this study may include to society, knowledge, and/or direct benefit to the subjects.

Please note that compensation cannot be a potential benefit for participating in the study.

For all Aims, there are no anticipated direct benefits of the research to subjects. Potentially, an indirect benefit for RWPA clients included in study secondary analyses or focus groups (as well as other people with HIV [PWH]) would be improved health or well-being through the continual improvement of HIV services, based on findings from the proposed study. The analyses conducted and intervention strategies tested and refined as part of the proposed study may inform future programs, service delivery models, and policies. They may specifically support decisions that will maximize the efficiency of HIV service delivery for achieving and sustaining VS, in NYC and other jurisdictions.

Clients included in D2S reports delivered to their RWPA providers as part of the intervention may receive more rapid follow-up and assistance than they would in the absence of the intervention. They may indirectly benefit through supportive services delivered to reduce barriers to suppression, and through increased or accelerated ability to adhere to ART and achieve/maintain VS, and thus improve/maintain overall immunity and health.

Addressing barriers to VS may also indirectly improve overall quality of life. We expect that the barriers to be addressed will include individual and higher-level factors such as patient-provider relationships, mental health issues, substance use, unstable housing, and unemployment. It is possible that support-service providers will be able to mitigate or remove these barriers through, for example, placing clients in safe and stable housing and/or aiding in the transition to a preferred, culturally competent medical provider.

Providers participating in the focus groups, interviews, and DCEs will receive no direct benefits as targets of the D2S intervention, but there may be psychosocial benefits accrued by contributing to the improvement of the healthcare system. There may also be downstream improvements to organizational culture and job satisfaction (and prevention of burnout), due to being better able to care effectively for vulnerable/ unsuppressed PWH.

For the administrative supplement, there are no anticipated direct benefits of the research to subjects. Potentially, an indirect benefit for RWPA clients as well as other people with HIV (PWH) would be improved processes for the use of HIV-related data in program implementation and ending-the-HIV-epidemic/data-to-care/data-to-suppression activities, based on findings from the proposed study.

The activities to be conducted may inform future programs, service delivery models, and policies. They may specifically inform the integration of consumer perspectives in initiatives to improve HIV viral suppression, in NYC and other jurisdictions. The DD process may also empower RWPA clients and better engage RWPA clients in their own HIV care, by recognizing their autonomy and increasing their day-to-day control over the uses of their HIV laboratory data.

Q. Alternatives

Describe alternative therapies providing data to support their efficacy or lack of efficacy. An important alternative is also not to participate in this research.

The alternative to agreeing to participate is not to participate in the study. Care that patients receive at the program sites will not be affected by a decision to participate, withdraw or not participate in the study. Similarly, program staff

decisions to participate, withdraw or not participate will not affect their employment or Ryan White contract status with the DOHMH.

R. External Sites

☐ N/A

Please indicate all external parties that will be involved in the study. If investigators will be conducting research at one or more non-DOHMH site(s), additional information is required. This includes, but is not limited to, plans for authorization and/or IRB approval at each site, explanation of funding and organizational relationships, description of procedures at each site, and plans for data and safety monitoring. Details, as applicable to the various types of situations that may occur. Describe whether results will be shared with subjects or others (e.g., the subject's or their primary care physicians), and if so, describe how it will be shared. As applicable, this may include individual patient results (genetic testing), incidental findings, or overall study findings.

☐ External IRB Document(s) attached

☐ This research study involves a contract with an approved vendor

CUNY ISPH will function as the lead agency and academic partner for the proposed project, while DOHMH will serve as the subcontracting agency and government partner. DOHMH will conduct screening for purposive sampling (for focus groups), and will lead recruitment of both providers and patients through communications with its RWPA contractors, who are already in regular communication with DOHMH regarding their RWPA programs. ISPH will participate in final sampling decisions and in instrument/ discussion guide development, and will conduct focus groups and provider interviews. ISPH will also lead qualitative analyses and DCE survey analyses, though DOHMH analysts may contribute to qualitative focus group coding. DOHMH analysts will be the sole handlers of client-level BHHS secondary data sources. Both institutions will be responsible for the overall synthesis, interpretation, and dissemination of data, and the engagement of the AB. [name] of the DOHMH will function as the point person coordinating AB communications.

It is not expected that individual program sites (where some recruitment and data collection will take place) will require IRB approvals from their own agencies, since the agency staff will never be responsible for recruiting patients and collecting informed consent, nor will they be responsible for collecting or storing any study data. They will only be asked to support recruitment by the DOHMH-CUNY study team, through staff assistance with the initial introduction of the study opportunity and referring any willing focus-group participants to the study team (by providing study team members' contact details) for further communications. If those sites later determine there is a need to engage their agency IRBs, the DOHMH-CUNY study team will work closely with those sites to obtain and maintain their IRB approvals, and will restrict data collection falling under their IRBs to periods in which their IRB approvals are current/active.

DOHMH evaluation and quality management of RWPA programs are built into the services contract agreement with each RWPA-funded agency. The DOHMH is the RWPA Grantee (recipient of federal funds from HRSA) for the New York eligible metropolitan area, and is responsible for the contract administration, evaluation, planning and continual quality improvement of New York Ryan White Part A programs.

Results of the study will be shared only in the aggregate, with RWPA providers, patients/consumers, and HIV Health and Human Services Planning Council of NY members (representing a mix of patients/consumers, policy makers,

advocates, and service providers or administrators who partner with DOHMH in planning and decision-making related to Ryan White Part A services). More preliminary and in-depth presentations and discussion of study findings will take place in AB meetings, for the input and guidance of AB members, representing multiple stakeholder groups. In addition, study findings will be shared (also in the aggregate) beyond these local stakeholders, with other researchers, policy-makers, healthcare professionals, consumers, advocates and students or other interested audiences – at local, national and international conferences and in peer-reviewed journals.

S. NYC DOHMH as Lead Institution

☐ N/A

If NYC DOHMH will serve as the lead institution for a multi-site study, specific information about management of information related to safety of subjects must be provided. This includes, but is not limited to: 1) obtaining and maintaining IRB approval at each site; 2) ensuring that each site follows consent procedures and utilizes consent documents approved by the designated IRB (if the designated IRB is not the NYC DOHMH IRB, then the IRB-approved consent document must be similar to the NYC DOHMH IRB-approved consent document with regards the content and style of the document); and 3) plans for data and safety monitoring.

- ☐ Individual Investigator Agreement(s) attached
☒ IRB Authorization Agreement(s) attached

This is a multi-site study involving non-exempt human subjects research (HSR). In accordance with National Institutes of Health (NIH) policy, all sites confirm the use of a single Institutional Review Board (IRB).

Single IRB of Record: The New York City (NYC) Department of Health and Mental Hygiene (DOHMH) IRB will serve as the single IRB of record for the proposed study. The partnering institutions agree to this reliance upon the review of the DOHMH IRB. Participating NYC Ryan White Part A (RWPA) agencies will be advised of the DOHMH IRB's role as the IRB of record for this project, once the study is funded (expected July 2021), and the DOHMH IRB contact information will be included on all informed consent documents.

The DOHMH IRB is registered with the federal Office for Human Research Protections. The IRB that will review the protocol has appropriate membership, including the professional competence necessary to critically review the proposed research.

Communication Plan: As the institution housing the existing person-level and agency-level data sources to be leveraged for this study (e.g., HIV programmatic and surveillance datasets and RWPA HIV services contract documents) and the only institution storing participant personal identifiers, DOHMH will be the central point of contact for the IRB. As such, DOHMH commits to the following:

- Coordinate communication with other sites;
- Request and receive information and documents from relying sites;
- Develop template materials for review by the DOHMH IRB and for limited modification by other sites;

- Submit materials from all sites to the DOHMH IRB and coordinate responses to any IRB queries; and
- Provide documentation to other sites.

Other participating study sites will provide necessary information and assurances to the DOHMH for submission to the IRB. For example, all City University of New York (CUNY) Institute of Implementation Science in Population Health (ISPH) study team members and ISPH-hired consultants will be listed on the DOHMH IRB application, and their CVs and HSR certifications (CITI) will also be maintained up to date and filed with the DOHMH IRB. The DOHMH IRB will communicate directly with the study team as a proxy for all relying sites (e.g., CUNY ISPH).

Individual Authorization Agreement: All participating sites shall enter into and sign an institutional authorization agreement (IAA) prior to the initiation of the study, as has been done in our previous studies.

Recordkeeping: As the lead institution under the grant, ISPH will be responsible for maintaining records related to the fully executed IAA. ISPH will also be responsible for maintaining records related to the Communication Plan.

T. FUTURE RESEARCH

☒ N/A

Please indicate if there are plans to retain, maintain, use or share the information collected from this research study for future research. If applicable, please include a description of the types of research, period of time, and whether sharing or plans to make information publically available.

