unsuppressed clients with whom they already have established relationships around meeting nonmedical needs. Merging RWPA program data and surveillance data, DOHMH will generate site-specific reports twice per year, listing active RWPA behavioral health and housing program clients who lack evidence of VS for the past year. To hone sites' use of reports, DOHMH will: (1) conduct D2S site visits to engage staff at all levels,³² review D2S reports, guide site-specific root cause analyses,^{149,150} and develop quality improvement (QI) plans structured by the Model for Improvement;¹⁵¹ (2) convene provider learning groups for peer-to-peer sharing of D2S QI plans and best practices; (3) offer dedicated TA to carry out D2S QI projects, applying driver diagrams, process mapping and 'plan-do-study-act' cycles to assess project outcomes; and (4) coach sites for completion of final QI project reports and presentations at an annual "Power of QI" conference. This CB/TA approach is structured by the Model for Improvement but necessarily tailored to sites' challenges. DOHMH will also offer trainings/TA on accessing and reviewing D2S reports with other data sources (e.g., electronic health records [EHRs]) to triage cases for follow-up, and delivering patient navigation for PWH with mental health needs. Replication of CB/TA components will be facilitated by documentation on DOHMH's website for HIV provider training, CB/TA and other resources, including webinars for self-guided learning.¹⁵²

Specific aims. The D2S intervention will arm support-service staff with actionable client-level, surveillance-based VS status reports and capacity-building for targeted ART adherence support. We propose to scale and test the D2S intervention with 27 RWPA service agencies.

- Aim 1:** Measure D2S intervention effects on timely VS and time to VS, in a stepped-wedge hybrid Type 1 trial.
- Aim 2:** Identify modifiable determinants of D2S response, by comparing characteristics of D2S-exposed clients who do and do not achieve VS, to recognize opportunities to tailor and strengthen the intervention.
- Aim 3:** Assess D2S acceptability and participant preferences and priorities for its implementation, in eight (client and provider) focus groups and in a discrete choice experiment (DCE) with RWPA staff (n=200).

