Our proposed implementation science study applies experimental (Aim 1) and observational methods (Aims 1-3) to evaluate D2S intervention effectiveness and opportunities for refinement. In Aim 1, we employ a cross-sectional stepped-wedge, hybrid trial of D2S intervention effectiveness.³⁹ Hybrid designs have been used in a variety of clinical and support-service settings to simultaneously assess effectiveness and implementation.^{39,153-156} Their advantages include (1) incorporation of mixed-methods studies into RCTs to examine relationships between implementation and effectiveness and (2) the speed of translation of effective strategies into broader practice, facilitated by testing interventions in real-world settings from the outset.¹⁵⁷ Of the three hybrid design types, our proposed study applies Type 1: testing intervention effects while collecting data on implementation. To assess implementation processes and outcomes, we will review RWPA service data reported to DOHMH (follow-up with listed clients) and staff feedback on D2S reports and CB. Data on implementation will be collected in semi-structured interviews with 24 staff (from eight purposively sampled agencies) and tracking sheets (like the Companion Reports used in the D2S pilot), and will be reviewed alongside sites' RWPA service reporting. In Aim 2 secondary analyses, we will identify modifiable drivers of VS among previously unsuppressed PWH exposed to the D2S intervention. VS outcomes for Aims 1 and 2 will be derived from the NYC HIV surveillance registry. Client-level reporting by

DOHMH-funded programs will supply measures of potential VS drivers, including modifiable factors such as substance use and housing. Organizational factors (e.g., size, age, type)³² will be pulled from contract documents. Aim 3 focus groups will gather input on D2S and inform DCE design. The DCE will quantify preferences for D2S intervention features. We will use findings from all Aims to refine the intervention for NYC maintenance and for broad dissemination.

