Target Accrual: Aim 1: N≈24 staff participants in interviews. Aim 3: N≈72 staff and client focus group participants; N=200 staff participants in DCE surveys. Aim 1 secondary analyses (using observational data from existing sources) are expected to involve approximately 1,283 clients (counting those exposed and unexposed to the D2S intervention), based on preliminary data from eligible programs. Aim 2 secondary data analyses are expected to involve approximately 700 clients (based on the expected number to be exposed to the intervention in Periods 1 and 2 of the trial).

Administrative supplement: N≈50 clients will participate in the deliberative democracy (DD) sessions.

Anticipated Number of Charts to be Reviewed: N/A

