Clients to be included in the Aim 1 secondary analyses of the stepped-wedge trial of D2S will be identified through the analysis of merged programmatic (eSHARE) and surveillance (NYC HIV Registry) data, based on the eligibility criteria noted above (concerning enrollment status/timing, vital status and viral suppression [VS] status in a given reporting period). Additional data elements from the NYC HCV Registry will be incorporated into Aim 1 secondary analyses without the modification of existing inclusion/exclusion criteria. Clients to be included in Aim 2 secondary analyses of drivers of VS will represent a subset of clients analyzed for Aim 1 – specifically, those clients who were exposed to the D2S intervention during the course of the trial.

For Aim 3, recruitment for the focus groups is as follows: Primary data collection will include five focus groups with an average of nine providers each (N ≈ 45) and three additional focus groups with an average of nine clients each (N ≈ 27). Provider groups will be organized by setting (clinical versus non-clinical/CBO), and split within setting by program role: administrative (including information-technology/data managers and program directors or medical directors),

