Implementation outcome assessment will include primary data collection (24 in-depth interviews, each lasting up to 60 minutes) with providers at participating programs. Recruitment for each interview will take place using purposive sampling of RWPA service providers included in the trial. Study personnel will initially contact eligible, sampled providers to introduce the study and invite them to take part in an interview. If they agree, in advance of the interview, each provider will be taken through a detailed consent process. Interviews will be digitally recorded using password-protected devices or videoconferencing platform features. Recordings will be downloaded onto CUNY secure servers to be transcribed and analyzed (with help/context from session notes). Password-protected files with session content and summaries will be shared with DOHMH for DOHMH analysis as well. Each participant will receive a \$75 gift card for their participation.

Aim 2. Aim 1 results will be used to identify a cohort of RWPA clients exposed to D2S during the trial (those flagged as unsuppressed on D2S reports that were delivered to implementing sites), and distinguish those who did and did not achieve TVS, for assessment of modifiable determinants of the outcome (aside from the intervention, a condition shared by all clients included in Aim 2). As in Aim 1, Aim 2 will entail secondary analysis at the DOHMH of existing data sources that are already securely stored and routinely merged and analyzed at the DOHMH. We will utilize client-level HIV surveillance data, furnished to DOHMH as part of mandatory New York State (NYS) HIV reporting, and merged with routinely collected and evaluated client-level data from RWPA and Housing Opportunities for Persons with AIDS (HOPWA) programs; as well as RWPA agency-level and program-level data also housed at DOHMH and collected as

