Power Analyses for the Trial. Our power analyses are based on simulated D2S reports on earlier time periods, generated using available and complete merged surveillance and program data (through 2019 for D2S reports and through September 2020 for six-month follow-up, where follow-up begins two months following the end of a given report year). For the 26 sites and 48 programs originally expected to be included in the trial based on preliminary data, six rounds of baseline reports (on July 2016-June 2017, calendar year [CY] 2017, July 2017-June 2018, CY2018, July 2018-June 2019, and CY2019) list 1,283 unique clients who would be eligible for the trial if we imagine that trial as having a Period 0 starting in September 2017. When we allow clients to count in multiple periods, the 1,283 account for 1,782 potential trial outcomes; at baseline, ~43.7% of those outcomes are TVS (VS in a six-month period starting two months after the end of the report year in which clients were unsuppressed). Based on simulation studies using a mock pairing of sites and repeated randomization of sites within matched pairs, we estimate 80% power to detect an OR of 1.86 (RR of 1.35), corresponding to 59.1% achieving TVS with D2S, versus the base rate (43.7%). Due to the smaller N when we omit repeat observations, the sensitivity analysis will have lower statistical power than the primary analysis; however, preliminary calculations indicate that an OR ~2.08 (RR ~1.41) will be detectable. For the secondary endpoint, time to VS (with 12 months of follow-up), we will use Cox regression based on a model analogous to that used for TVS. Insofar as there will be more events for the secondary outcome than for TVS, and insofar as time-to-event analyses can be more powerful than binary outcome analyses, we expect power >80% to detect a doubling of the hazard ratio for the intervention versus control condition.

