Qualitative Analysis. Interviews will be audio-recorded and transcribed. Thematic analysis will be conducted in Dedoose using a ‘framework fit’ technique, applying pre-defined codes derived from CFIR and RE-AIM. We will also use grounded exploration to interpret categories’ meaning and attend to emergent themes salient to participants. This combined inductive-deductive approach suits the structured nature (well-defined domains) of the implementation science (IS) frameworks being applied. Initial codes will be identified by independent review of three transcripts by two study team members in dialogue with the senior qualitative methods advisor. The draft codebook will then be independently applied to a single transcript, with discrepancies resolved in consensus sessions to optimize inter-rater reliability, yielding a final codebook to be applied to the entire dataset. Also in this phase, we will use process analysis to map implementation trajectories by program as a means of comparing programs’ intervention uses, which may be associated with programs’ better or worse outcomes. Qualitative and quantitative analyses will be integrated by examining thematic patterns reflecting RE-AIM and CFIR implementation constructs as they explain client and organizational outcomes across programs. Aim 1 qualitative and quantitative phases will proceed concurrently, with the qualitative analysis serving a primarily explanatory function in relation to quantitative findings, while also having direct applications in terms of informing future refinements to the D2S intervention to optimize implementation and sustainability.

AIM 2.

Overview. We will create a retrospective, unduplicated cohort of unsuppressed clients exposed to the D2S condition in order to identify modifiable determinants of D2S response. VS outcome data for Aims 1 and 2 will be derived from the Registry. Client-level DOHMH-funded program reporting will supply measures of potential VS determinants, including modifiable factors such as substance use and housing stability – assessed semi-annually in RWPA. Organizational factors will be pulled from agency contract documents.

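### Aim 2 targets determinants of D2S response, but its exposed-only odds ratios mix prognosis for suppression with modification of the D2S effect and cannot separate them

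*Combined protocol and SAP*

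**What the plan says.** The target appears in two places. The Specific aims give Aim 2 as: "Identify modifiable determinants of D2S response, by comparing characteristics of D2S-exposed clients who do and do not achieve VS". The Aim 2 Overview in section K repeats it: "We will create a retrospective, unduplicated cohort of unsuppressed clients exposed to the D2S condition in order to identify modifiable determinants of D2S response".

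Other sections use a weaker target. The design summary after the Specific aims says "we will identify modifiable drivers of VS among previously unsuppressed PWH exposed to the D2S intervention". Section J speaks of determinants of the outcome, and the section K Analysis Plan of modifiable factors for TVS.

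The cohort is exposed-only throughout. Section G describes it as a subset of the Aim 1 clients: "specifically, those clients who were exposed to the D2S intervention during the course of the trial". Section J says the determinants are sought "aside from the intervention, a condition shared by all clients included in Aim 2".

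The Aim 2 Analysis Plan (section K) is a logistic regression of TVS on client and organizational factors, adjusted for demographics and Period (1 or 2), with generalized estimating equations for clustering by agency. It has no D2S term and no factor-by-D2S term. The only interactions Aim 1 considers are site-by-intervention and period-by-intervention.

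Unexposed clients are already in the trial data. Section E counts "approximately 1,283 clients (counting those exposed and unexposed to the D2S intervention" for Aim 1, and section J places unexposed observations at all 27 agencies in Period 0 and at the delayed agencies in Period 1.

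**The concern.** Read as an effect, response to D2S is the difference in suppression that D2S makes. Whether a factor is a determinant of that response depends on whether the difference varies with the factor, so clients with and without D2S have to be compared. When all clients are exposed, two kinds of factor can look alike. One lowers suppression equally with and without D2S. The other changes how well D2S works.

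The Specific aims and section K intend the Aim 2 results for tailoring and strengthening D2S and for extending its benefit to more client subgroups. A reader given these ORs as determinants of D2S response could take an ordinary prognostic factor as a sign that D2S works poorly in that group. The same reader could overlook a barrier that D2S in fact removes.

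**Working it through.** **Inputs from the documents.** TVS without D2S is 43.7% (section K, Retrospective Analyses). TVS at the detectable OR of 1.86 is 59.1% (Power Analyses for the Trial). About 700 unduplicated clients are exposed (Aim 2). For the trial as a whole, "the 1,283 account for 1,782 potential trial outcomes".

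**The plan's own figure.** The control odds are 0.437/0.563 = 0.776. Then 0.776 × 1.86 = 1.444 and 1.444/2.444 = 59.1%. The stated rate reproduces.

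**Share of exposed suppressors who would have suppressed anyway.**
- If D2S prevents no one's suppression: 0.437/0.591 = 74%.
- Without that assumption, the two marginal rates allow anything from (0.437 + 0.591 − 1)/0.591 = 5% up to 74%.

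**What exposed-only ORs can show.** These are illustrations with assumed factor frequencies and ORs: N = 700, two-sided 0.05, no inflation for clustering.
- *Prognostic only.* A factor has OR 1.65 for TVS in both conditions, so it does not change the D2S OR. With reference-group TVS of 43.7% to 59.1%, the exposed-only test is significant 76% to 81% of the time at 25% factor frequency, and 88% to 91% at 50%. A factor-by-D2S test would flag it 5% of the time.
- *Masked modifier.* A barrier has OR 0.6 without D2S and D2S removes it fully, so its OR among the exposed is 1.0. The exposed-only test flags it 5% of the time. An interaction test (ratio of ORs 1/0.6 = 1.67), with 583 to 1,082 unexposed and factor frequency 25% to 50%, has about 50% to 75% power.

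**Precision of a factor-by-D2S term.** Take f as the factor frequency and P as the TVS rate, with E for exposed and U for unexposed. The variance of the log ratio of ORs is about 1/[n_E P_E(1−P_E) f(1−f)] + 1/[n_U P_U(1−P_U) f(1−f)]. With similar P(1−P), its standard error (SE) relative to the exposed-only log OR is √(1 + n_E/n_U).
- *Pooled, unique clients:* n_U = 1,283 − 700 = 583, giving √(1 + 700/583) = 1.48.
- *Pooled, outcomes:* n_U = 1,782 − 700 = 1,082, giving √(1 + 700/1,082) = 1.28.
- *Detectable ratio, pooled:* at 25% frequency and 80% power, about 1.9 to 2.1. Power for a ratio of 1.65 is 48% to 60%.
- *Period 1 only:* with equal periods, 1,782/3 = 594 outcomes each, so Period 1 has about 297 exposed and 297 unexposed. Exposed outcomes over the trial are 297 + 594 = 891. The SE ratio is √(2 × 891/297) = √6 = 2.4.
- *Detectable ratio, Period 1 only:* at f = 0.25 the variance is 1/(297 × 0.2417 × 0.1875) + 1/(297 × 0.2460 × 0.1875) = 0.147, so the SE is 0.384 and exp(2.80 × 0.384) is about 2.9, before clustering.

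The Period 1 case matters because Period 0 is entirely unexposed and Period 2 entirely exposed. Without factor-by-period terms, any drift over time in a factor's association with TVS loads onto the factor-by-D2S term.

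**The case against.** The strongest reply is that this is largely a label. The plan does not define response as a causal difference, and the same sentence of the Specific aims describes the comparison actually made. Three other places name a target that the analysis can estimate, and section J is open that exposure is shared. Much of this stands. Rewording two sentences would remove the inconsistency, and a barrier still linked to non-suppression under D2S is useful to know whether or not it modifies the effect. Refinement also draws on all three aims.

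The reply does not remove the point. The stated aim, in both places, is D2S response, and nothing else in the plan tests whether client-level factors modify the effect.

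A reader might go further than the documents allow in three ways.
- *That Aim 2 can find only general correlates of suppression.* Exposed-only ORs also carry effect modification; they just cannot isolate it. Factors that exist only under D2S, such as report use or training uptake, can be studied only among the exposed.
- *That 74% of responders would have suppressed anyway, as a finding.* It is an upper bound from two marginal rates at one effect size, and 59.1% is the detectable rate, not a forecast.
- *That one added interaction term settles who benefits.* With only period terms and a clustering adjustment it is open to the drift described above. It also ignores the matching, which the Viral Suppression Analysis Plan says should be conditioned upon. A series of such tests would be underpowered.

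**Conclusion.** The point holds as a mismatch between the stated target and the analysis. The planned ORs describe which exposed clients reach TVS; they do not show what determines the effect of D2S. The remedy is inexpensive and changes what Aim 2 can conclude, so it should be made.

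The mismatch itself needs no numerical assumption. The 74% needs D2S to prevent no one's suppression and the true effect to equal the detectable one; under the first assumption, a smaller effect would raise the share. The significance and power figures rest on illustrative ORs and frequencies with independent observations. The unexposed counts come from subtraction and are approximate, because clients can contribute under both conditions while the Aim 2 cohort is unduplicated. The 2.4-fold figure assumes equal periods of 594 outcomes with Period 1 split evenly.

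**What to change.** 1. Reword Aim 2 in the Specific aims and in the section K Overview. Report the exposed-only ORs as correlates of TVS among D2S-exposed clients, in line with the design summary, section J and the Analysis Plan. Keep this analysis, including for factors that exist only under D2S.
2. For factors measured in both conditions, add an exploratory model on all trial observations (Periods 0 to 2) with D2S, the factor, D2S-by-factor, period, and agency or pair terms, allowing for clustering by agency. Add a sensitivity analysis with factor-by-period terms, so that the contrast rests on the concurrent randomized comparison in Period 1.
3. Present the ratios of ORs with 95% confidence intervals as the evidence on D2S response, not as pass/fail tests.

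The cost is SAP text and two further models per factor (the main one and its sensitivity version), using program, registry and contract data that the health department already holds and merges. The drawback is the low precision shown above: many intervals will be wide, especially in the sensitivity analysis, and the text should say so in advance.
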